#### CONFIDENTIAL AND PROPRIETARY

## **Clinical Protocol - Device**

A Prospective Multi-Centre Study in Patients Undergoing Total Knee Replacement Version: 2.0, 02Jun2021 with JOURNEY II CR Total Knee System Page: 56 of 57

g. New information: if new information becomes available that can significantly affect a subject's future health and medical care, that information shall be provided to the subject(s) affected in written form. If relevant, all affected subjects shall be asked to confirm their continuing consent in writing.

Study Number: Journey II CR.2020.11

- h. ensure compliance with the applicable regulatory requirements and ethical principles for the process of obtaining informed consent, and
- i. ensure and document appropriate training if an authorized designee is appointed to conduct the informed consent process.
- 6. Compliance with the protocol. The Principal Investigator shall:
  - a. indicate his/her acceptance of the protocol in writing,
  - b. conduct the clinical investigation in compliance with the protocol,
  - c. create and maintain source documents throughout the clinical investigation and make them available as requested during monitoring visits or audits,
  - d. ensure that the investigational device is used solely by authorized users as specified in 6.2, and in accordance with the protocol and instructions for use,
  - e. propose to the Sponsor any appropriate modification(s) of the protocol or investigational device or of the use of the investigational device,
  - f. refrain from implementing any modifications to the protocol without agreement from the Sponsor, IEC and regulatory authorities, if required,
  - g. document and explain any deviation from the approved protocol that occurred during the course of the clinical investigation,
  - h. ensure that an adequate investigation site team and facilities exist and are maintained and documented during the clinical investigation,
  - i. ensure that maintenance and calibration of the equipment relevant for the assessment of the clinical investigation is appropriately performed and documented, where applicable,
  - j. ensure the accuracy, completeness, legibility, and timeliness of the data reported to the Sponsor in the CRF and in all required reports,
  - k. maintain the device accountability records,
  - 1. allow and support the Sponsor to perform monitoring and auditing activities,
  - m. be accessible to the monitor and respond to questions during monitoring visits,
  - n. allow and support regulatory authorities and the IEC when performing auditing activities,
  - o. ensure that all clinical-investigation-related records are retained as required taking measures to prevent accidental or premature destruction, and
  - p. review and sign the clinical investigation report, as applicable.
- 7. Medical care of subjects. The Principal Investigator shall
  - a. provide adequate medical care to a subject during and after a subject's participation in a clinical investigation in the case of adverse events.
  - b. inform the subject of the nature and possible cause of any adverse events experienced,
  - c. provide the subject with the necessary instructions on proper use, handling, storage, and return of the investigational device, when it is used or operated by the subject,
  - d. inform the subject of any new significant findings occurring during the clinical investigation, including the need for additional medical care that may be required,
  - e. provide the subject with well-defined procedures for possible emergency situations related to the clinical investigation, and make the necessary arrangements for emergency treatment, including decoding procedures for blinded/masked clinical investigations, as needed,
  - f. ensure that clinical records are clearly marked to indicate that the subject is enrolled in a particular clinical investigation,

#### CONFIDENTIAL AND PROPRIETARY

## **Clinical Protocol - Device**

A Prospective Multi-Centre Study in Patients Undergoing Total Knee Replacement Version: 2.0, 02Jun2021 with JOURNEY II CR Total Knee System Page: 57 of 57

g. if appropriate, subjects enrolled in the clinical investigation shall be provided with some means of showing their participation in the clinical investigation, together with identification and compliance information for concomitant treatment measures (contact address and telephone numbers shall be provided),

Study Number: Journey II CR.2020.11

- h. inform, with the subject's approval or when required by national regulations, the subject's personal physician about the subject's participation in the clinical investigation, and
- i. make all reasonable efforts to ascertain the reason(s) for a subject's premature withdrawal from the clinical investigation while fully respecting the subject's rights.
- 8. Safety reporting. The Principal Investigator shall\*:
  - a. record every adverse event and observed device deficiency, together with an assessment,
  - b. report to the Sponsor, without unjustified delay, all serious adverse events and device deficiencies that could have led to a serious adverse device effect; this information shall be promptly followed by detailed written reports, as specified in the protocol,
  - c. report to the IEC serious adverse events and device deficiencies that could have led to a serious adverse device effect, if required by the national regulations or protocol or by the IEC,
  - d. report to regulatory authorities, serious adverse events and device deficiencies that could have led to a serious adverse device effect, as required by the national regulations, and
  - e. supply the Sponsor, upon Sponsor's request, with any additional information related to the safety reporting of a particular event.

#### CONFIDENTIAL AND PROPRIETARY

\*To the extent outlined in section 12.

1 LIST OF ABBREVIATIONS

ADE	
ADE	Adverse Device Effect(s)
AE	Adverse Event(s)
AVN	Avascular Necrosis
BCS	Bi-cruciate Stabilized
CRF	Case Report Form(s)
CR	Cruiciate Retaining
CRO	Contract Research Organization
CV	Curriculum Vitae
DA	Degenerative Arthriti
DD	Device Deficiency(ies)
DFMEA	Design Failure Mode Effects Analysis
FAS	Full Analysis Set Population
FDA	Food and Drug Administration
FU	Follow-Up
GCP	Good Clinical Practice
нто	High Tibial Osteotomy
ICH	International Conference on Harmonisation
IEC	Independent Ethics Committee
IFU	Instructions for Use

CONFIDENTIAL AND PROPRIETARY

Statistical Analysis Plan

A Prospective Multi-Centre Study in Patients Undergoing Total Knee Replacement with JOURNEY II CR Total Knee System Number: Journey II

CR.2020.11 ST: ST1197

Version: V1.0, 20-MAY-

2024

Page: 4 of 20

Abbreviation	Definition
IP	Investigational Product
IRB	Institutional Review Board
ISF	Investigator Site File
ITT	Intention to Treat population
KSS	Knee Society Score
LOCF	Last Observation Carried Forward
NA or N/A	Not Applicable
N (or n)	Total Sample Size (or subgroup sample size)
NSAID	Nonsteroidal Anti-inflammatory Drug
OA	Osteoarthritis
OKS	Oxford Knee Score
PI	Principal Investigator
PMA	Pre-Market Authorization
PP	Per-protocol Population
PTA	Post Traumatic Arthritis
RA	Rheumatoid arthritis
RCT	Randomized Controlled Trial
ROM	Range of Motion
S+N	Smith&Nephew.Inc
SADE	Serious Adverse Device Effect(s)
SAE	Serious Adverse Event(s)
SAF	Safety population
SAP	Statistical Analysis Plan
SoC	Standard of care
THA	Total Hip Arthroplasty
TKA	Total Knee Arthroplasty

CONFIDENTIAL AND PROPRIETARY

Statistical Analysis Plan

A Prospective Multi-Centre Study in Patients Undergoing Total Knee Replacement with JOURNEY II CR Total Knee System Number: Journey II

CR.2020.11 ST: ST1197

Version: V1.0, 20-MAY-

2024

Page: 5 of 20

Abbreviation	Definition
USADE	Unanticipated Serious Adverse Device Effect(s)
WOMAC	Western Ontario and McMaster Universities Arthritis

2 INTRODUCTION

The following Statistical Analysis Plan (SAP) details the statistical considerations, including the data analysis methods, for the Study Protocol Journey II CR.2020.11, Version 2.0, 02Jun2021. Related documents to this SAP are the Study Protocol, Case Report Form (CRF), and Tables, Figures and Listings (TFL) Templates Shells.

3 STUDY DESIGN

This study is a prospective, non-randomized multi-centre study to evaluate the performance of JOURNEY II CR Total Knee System in APAC patient populations, also to evaluate impact of patella resurfacing on the outcomes of JOURNEY II TKA. Totally up to 15 sites will participate within India, China mainland, Hongkong, Singapore, Thailand and Japan. Totally up to 480 knees information will be collected.

The decision on whether to resurface patella or not will be made by investigator based on patient's conditions.

CONFIDENTIAL AND PROPRIETARY

Statistical Analysis Plan

A Prospective Multi-Centre Study in Patients Undergoing Total Knee Replacement with JOURNEY II CR Total Knee System

Number: Journey II

CR.2020.11 ST: ST1197

Version: V1.0, 20-MAY-

2024

Page: 6 of 20

STUDY SCHEDULE

Schedule of Events [†]	Pre-Operative -28 to 0 days	Operation Day 1	Immediate Post - op to 6 weeks Post-Op (Day 1 to 6 weeks+14 days)	6 months Post-Op (± 14 days)	l year Post-Op (± 30 days)	2 years Post-Op (± 60 days)	3 years Post-Op (± 60 days)
Informed Consent	x						
Inclusion/Exclusion	x		18		· ·	46	1
Demographics/Medical History	x				6		
Operative Data Collection	**	х			N :		
Discharge Data Collection	*		x		 		
OKS ³	x		15	x	x	x	x
FJS ²	*		1	x	x	x	x
KSS ²	x		10 0	x	x	x	x
Patient Expectation	x		1		*		
Patient Satisfaction ²	9		12	x	x	x	x
Quantitative Radiographic Assessment	x³		x ⁴	x ⁵	X ⁵	x ⁵	2.40
Safety Assessment (AEs, DDs)		х	х	х	x	x	x
End of Study/Exit	*	X ⁶	x ⁶	X ⁶	X ⁶	X ⁶	x

4 STUDY OBJECTIVES

The objectives of the study are listed as below,

- 1. Evaluate performance of JOURNEY II TKA in APAC patient populations
- 2. Evaluate impact of patella resurfacing on the outcomes of JOURNEY II TKA

5 STUDY ENDPOINTS 5.1 Primary Endpoint(s)

The primary endpoint for the study is defined as the OKS at 2 years.

CONFIDENTIAL AND PROPRIETARY

Statistical Analysis Plan

A Prospective Multi-Centre Study in Patients Undergoing Total Knee Replacement with JOURNEY II CR Total Knee System Number: Journey II

CR.2020.11 ST: ST1197

Version: V1.0, 20-MAY-

2024

Page: 7 of 20

5.2 Secondary Endpoint(s)

The following secondary endpoints have been defined for this study as below,

- OKS
- FJS
- KSS
- Patient Expectation
- Patient Satisfaction
- Radiographic Assessment

5.3 Safety Endpoint(s)

- •All adverse events (AEs) including intra-operative adverse events and complications
- Device related re-intervention
- Device Deficiencies

6 STATISTICAL CONSIDERATIONS

6.1 Determination of Sample Size

The sample size is established primarily using a precision of estimates-based approach for resurfaced and unsurfaced Patella cohorts separately. As a secondary concern formal statistical hypothesis testing to assess differences between the cohorts will be a possibility.

Based on an underlying assumption of standard deviation of 7.4 in OKS reported in literature (Bohm et al 2012)., a minimum of 192 knees are required, per cohort, to ensure that there is an 80% probability that a 95% confidence interval constructed around the OKS score can be calculated to within ± 1.2 units for each cohort of resurfaced and unresurfaced knees. To allow for up to 20% attrition during the data collection activity, this will be inflated to enrol a minimum of 240 knees per cohort.

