#### CONFIDENTIAL AND PROPRIETARY

**Clinical Protocol - Device** 

Study Number: Journey II CR.2020.11

A Prospective Multi-Centre Study in Patients Undergoing Total Knee Replacement Version: 2.0, 02Jun2021 with JOURNEY II CR Total Knee System

Page: 8 of 57

1. All the data will be collected based on knee, except inform consent, inclusion/exclusion and demographic/medical history.

- Patient reported outcome can be assessed and collected remotely for follow-up period.
- The radiographic images prior to 3 months can be accepted for pre-operative screening data due to hospital's SoC.
- Radiographic assessment can be conducted at discharge if it's the SoC of the site.
- Radiographic images can be retrieved from other hospital/facility under specific image acquisition protocol and send back to site for assessment.
- Exit form to be completed at the point of withdrawal if the study is not completed.

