6.3 Interim Analysis

The protocol stated an interim analysis was planned after the 2 year visit. However due to premature termination of the study no interim analyses will be performed.

7 STATISTICAL ANALYSIS 7.1 General

Smith+Nephew's Global Biostatistics group will conduct the statistical analysis for this study. Unless otherwise stated, all significance tests and hypothesis testing will be two-sided, performed at the 5% significance level. Resulting p-values will be quoted and 95% two-sided confidence intervals will be generated where appropriate. All p-values will be rounded to three decimal places, p-values less than 0.001 will be presented as '<0.001' in all tables.

Where data summaries are specified, categorical and ordinal variables will be summarized with frequencies and percentages. Continuous variables will be summarized with the following summary statistics: number of observations, mean, median, standard deviation, minimum and maximum values. All analyses will be performed in SAS 9.4 (or later).

All table summaries will be provided overall, and by surgical method (resurfaced/un-resurfaced patella).

Example mock shells are provided below:

Table: Demographics by subject				
		Resurfaced Patella	Un-Resurfaced Patella	Overall
Age	Mean			
	Median			
	Std			
	Min			
	Max			
	Q1			
	Q3			
	Inter Quartile Range			
	N			
Age	<65			

CONFIDENTIAL AND PROPRIETARY

Statistical Analysis Plan

Number: Journey II

CR.2020.11 ST: ST1197

Version: V1.0, 20-MAY-

2024

Page: 9 of 20

A Prospective Multi-Centre Study in Patients Undergoing Total Knee Replacement with JOURNEY II CR Total Knee System

>=65		
N		

PROM by knee				
Assessment		Resurfaced Patella	Un-Resurfaced Patella	Overall
Pre-Operative	Mean			
	Median			
	Std			
	Min			
	Max			
	Q1			
	Q3			
	Inter Quartile Ran	nge		
	N			
6 Month				
1 Year				
2 Year				
3 Year				

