7.10 Analysis of Primary Endpoint(s)

The protocol states:

CONFIDENTIAL AND PROPRIETARY

Statistical Analysis Plan

A Prospective Multi-Centre Study in Patients Undergoing Total Knee Replacement with JOURNEY II CR Total Knee System Number: Journey II

CR.2020.11 ST: ST1197

Version: V1.0, 20-MAY-

2024

Page: 17 of 20

The primary endpoint of this study is the OKS at 2 years. If we assume the mean of OKS at 2 years for the subjects with implant JOURNEY II TKA with and without Patella Resurfaced as $\mu 1$ and $\mu 2$. The hypothesis test will be as following:

H0: μ 1 = μ 2 vs

H1: $\mu 1 \neq \mu 2$

The mean difference (μ 1- μ 2) and 95% CI will be estimated. If zero is included in 95% CI of mean difference, then null hypothesis will be accepted, which means patella resurfacing has no impact on the outcomes of JOURNEY II TKA. Otherwise if zero is not included in 95% CI of mean difference, then alternative hypothesis (H1) will be accepted, which means patella resurfacing has significant impact on the outcomes of JOURNEY II TKA. If the lower limit of 95% CI is greater than 0, which means that the subject implant with Patella Resurfaced has higher OKS at 2 years. If the upper limit of 95% CI is less than 0, which means that the subject implant with Patella Resurfaced has lower OKS at 2 years.

In addition, the mean and 95% CI of OKS at 2 years for subjects implant with and without Patella Resurfaced will be estimated separately.

At time of writing the SAP, this study has been early terminated, the study no longer has sufficient power for this hypothesis test to be relevant and it will therefore not be performed. Summary statistics, 95% CI for $\mu 1$ and $\mu 2$ would be presented.

The primary endpoint will be summarized using the SAF population only due to premature termination.

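### The precision statement does not reproduce: the stated inputs need 163 knees per cohort for ±1.2 OKS, and 192 knees correspond to ±1.1 (a conservative error)

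*SAP*

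**What the plan says.** SAP 6.1 sizes the study on precision rather than power: "The sample size is established primarily using a precision of estimates-based approach for resurfaced and unsurfaced Patella cohorts separately". The variability input is given as follows: "Based on an underlying assumption of standard deviation of 7.4 in OKS reported in literature". The result is that "a minimum of 192 knees are required, per cohort, to ensure that there is an 80% probability that a 95% confidence interval" for OKS "can be calculated to within ± 1.2 units for each cohort of resurfaced and unresurfaced knees". The 192 is then inflated for 20% attrition to 240 knees per cohort. Protocol 11 makes the same statement with the same figures. SAP 7.1 sets the sidedness of the intervals: "95% two-sided confidence intervals will be generated where appropriate".

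Two other places bear on the point. Footnote 1 to the protocol's Study Schedule makes the knee the unit of data collection: "All the data will be collected based on knee, except inform consent, inclusion/exclusion and demographic/medical history". SAP 7.10 records that "this study has been early terminated, the study no longer has sufficient power for this hypothesis test to be relevant"; it drops the test and keeps summary statistics with a 95% CI for each cohort mean.

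**The concern.** The sentence gives four linked quantities: cohort size, SD, probability and half-width. With the confidence level fixed at 95%, any three determine the fourth, so the claim can be tested from the page. It fails the test. The cohort size is too large for the stated half-width and probability, by more than rounding explains.

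This sentence is the only numerical justification for 192 and 240 in either document. With the hypothesis test dropped, the 95% CI for each cohort mean is what remains of the primary analysis, so planned per-cohort precision is the design property a reader would compare it with. At stake is a design statement that cannot be reproduced and may be carried into the report. The cohorts themselves are not at risk of being too small for ±1.2 if knees are independent.

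**Working it through.** **Inputs.** SD 7.4, 192 knees per cohort, 80% probability and half-width 1.2 (SAP 6.1, Protocol 11); two-sided 95% interval (SAP 7.1); 20% attrition (SAP 6.1). Knees are treated as independent, because no clustering allowance is stated.

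**Formula.** The half-width is t·S/√n, where S is the sample SD and t is the 97.5% point of the t distribution on n−1 degrees of freedom. Since (n−1)S²/7.4² is chi-squared on n−1 degrees of freedom,

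P(half-width ≤ h) = P(χ²[n−1] ≤ n(n−1)h² / (t²·7.4²)).

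The required n is the smallest for which this reaches 0.80.

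**The plan's own figure.**

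| n | h | t | chi-squared bound | Probability |
|---|---|---|---|---|
| 162 | 1.2 | 1.9748 | 175.87 | 79.99% |
| 163 | 1.2 | 1.9747 | 178.07 | 81.64% |
| 192 | 1.2 | 1.9725 | 247.87 | 99.65% |
| 191 | 1.1 | 1.9725 | 206.09 | 79.88% |
| 192 | 1.1 | 1.9725 | 208.28 | 81.39% |

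The minimum for ±1.2 is 163, not 192. The gap is 29 knees: 192/163 = 1.178, so the stated figure is 18% above the computed one. A simulation of 400,000 draws at n = 192 gave 99.7% for ±1.2. Conditioning on the interval covering the true mean leaves both minima unchanged (163 for ±1.2, 192 for ±1.1).

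**What 192 does correspond to.** The half-width assured with 80% probability at n = 192 is

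(1.9725 × 7.4/√192) × √(207.23/191) = 1.0534 × 1.0416 = 1.097,

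where 207.23 is the 80% point of chi-squared on 191 degrees of freedom. At n = 191 it is 1.1002. Only half-widths between about 1.0972 and 1.1002 have 192 as their minimum. A target of ±1.15 needs 176.

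**Attrition.** 192/(1 − 0.20) = 240, which reproduces. The fault lies in the precision sentence alone. For comparison, 163/0.80 = 203.75, or 204 knees per cohort.

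**Other readings of ±1.2 at SD 7.4.**

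| Reading | Minimum n |
|---|---|
| Expected precision only, no assurance (normal formula) | 147 |
| Width and coverage jointly at 80% (0.95 × P ≥ 0.80) | 165 |
| Both cohorts jointly at 80% (P² ≥ 0.80) | 169 |
| 90% probability | 170 |
| 95% probability | 176 |
| 99% probability | 187 |

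None gives 192.

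**Unstated inputs that would give 192.** These are assumptions; none is in the documents.

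- An SD of 8.08 to 8.09 with ±1.2.
- A design effect of about 1.18 for paired knees. Write it as 1 + p·ρ, with p the share of knees from subjects who have both knees in the cohort and ρ the within-subject correlation. This needs p·ρ of about 0.178: ρ of 0.89 at p = 20%, 0.59 at p = 30%, or 0.36 at p = 50%.
- A further 15% allowance before the 20% attrition: 163/0.85 = 191.8, rounded up to 192.
- A one-sample calculation with 80% power for a difference of 1.5, which also gives 192. The text describes precision rather than power, and 1.5 appears nowhere.

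**The case against.** The strongest reply is that 192 knees do satisfy ±1.2 with at least 80% probability, so the sentence promises nothing the design fails to deliver. That is true of adequacy. It does not rescue the wording, which presents 192 as the minimum required and 80% as the probability attached to it; under the stated inputs both are wrong.

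A second reply is that an allowance may have been made and not written down, in which case the fault is incomplete reporting rather than arithmetic. This stands as a possibility. Several unstated routes lead to 192, so the exact match at ±1.1 does not prove that ±1.2 is a misprint. It is why the sponsor should check the source calculation rather than simply substitute ±1.1.

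A third reply is that the SAP was written after early termination, testing has been dropped, and the achieved intervals will supersede planned precision. This limits the consequence and is accepted. The SAP nevertheless repeats the sentence as current text, and correcting it costs almost nothing.

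**Conclusion.** The concern holds. At SD 7.4, with a two-sided 95% t-interval and 80% probability, ±1.2 needs 163 knees per cohort; the stated 192 is the minimum for ±1.1 and meets ±1.2 with 99.65% probability. The result assumes independent knees and normally distributed scores, as the chi-squared formula requires. Which input is wrong cannot be settled from the documents, and ±1.1 is an inference.

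The error is conservative. Under independence the planned cohorts exceed what ±1.2 needs, and no planned analysis or result changes. The harm is confined to a sample-size justification that a reader cannot reproduce. The correction should be made, but it does not threaten the study's conclusions.

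**What to change.** The sponsor should retrieve the original calculation and correct SAP 6.1 in one of two ways:

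- restate the planned precision as ±1.1 OKS units with 80% probability at SD 7.4 and 192 knees; or
- keep ±1.2 and state the input or allowance that leads to 192, such as a larger SD or a design effect for subjects contributing two knees, with its value and basis.

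In either case, name the formula or software, keep 192 and 240, and label the figure as planned precision, because the study ended early and the achieved intervals will depend on the knees observed. Add a note that the same sentence in Protocol 11 is affected.

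The cost is a clarifying sentence in the SAP or the report. Enrolment and the analyses are unaffected.

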6.2 Randomisation

No randomization has been planned for this study. The decision on whether to resurface patella or not will be made by investigator based on patient's conditions.

CONFIDENTIAL AND PROPRIETARY

Statistical Analysis Plan

A Prospective Multi-Centre Study in Patients Undergoing Total Knee Replacement with JOURNEY II CR Total Knee System Number: Journey II

CR.2020.11 ST: ST1197

Version: V1.0, 20-MAY-

2024

Page: 8 of 20

